5.1 General statistical methods

The statistical analyses will be presented by treatment group for the different analysis populations as defined in section 4 Analysis Populations.

Summary tables will usually be structured with a column for each treatment in the order Beriplex[®] P/N (Kcentra) and OCTAPLEX. For demographic and background characteristics a "Total" column will be additionally provided.

In general, continuous variables will be summarized using descriptive statistics, i.e. generally displaying number of patients in the respective analysis population, number of patients with data, number of patients with missing values, mean, standard deviation, minimum, lower quartile, median, upper quartile, and maximum.

Categorical variables will be summarized by using frequency counts and percentages. In addition, the number of patients with missing values will be displayed. Percentages usually relate to the number of patients with data. This includes data obtained by the respective missing data replacement strategy (see section 5.4 Missing data).

Means, medians, and standard deviations will be presented by 1 additional decimal place than the standard presentation level of the respective patient data. Minimum and maximum values will be presented using the same number of decimal places as the patient data. Percentages will be presented to 1 decimal place if not otherwise stated.

In listings, data will be sorted by treatment, site, and patient, and when appropriate by visit or other identifiers for sequence or type of observation.

If not otherwise specified, all statistical tests will be two-sided. The significance level of one sided tests will be divided by two to ensure comparability with two-sided tests.

The confidence level for calculation of confidence intervals will be chosen as (1-significance level) of the respective statistical test.

5.2 Strataaphar

Treatment allocation by the IRT will be stratified according to the following three parameters, documented as baseline prior to randomization.

History of TEE

Presence or absence of any embolic or thrombotic event, defined according to the Standardized MedDRA query (SMQ) "Embolic and thrombotic event", in the medical history of the patient.

Type of surgery

The type of surgery will be categorized into one of the following: "orthopaedic surgery", "cardiothoracic surgery" or "other surgery".

Expected Blood Loss

Expected blood loss will be categorized into one of the following: "
200 mL", "
100 mL but <200 mL" or ">50 mL but <100 mL".

5.3 Subgroups

The following subgroups will be defined:

- 1. expected blood loss ("≥200 mL", "≥100 mL but <200 mL" or "≥50 mL but <100 mL") according to information provided at randomisation
- 2. gender (male/female)
- 3. baseline INR (2 to <4 / 4 to $<6 / \ge 6$)
- 4. concomitant treatment with vitamin K (yes/no)
- 5. any TEE in medical history (yes/no)
- 6. occurrence of any TEE within 1 year prior to surgery (yes/no)
- ten permission. w" 7. type of planned surgery ("orthopaedic surgery", "cardiothoracic surgery" or "other Lite without surgery")
- 8. age in years (<=60, 60+)
- 9. race

To study the sensitivity of the efficacy results subgroup analysis will be performed for the primary and the secondary efficacy endpoints for the first four subgroups. Results for the different subgroups will be presented descriptively by presenting the results separately for each subgroup and its complement.

These subgroup analyses are considered to be exploratory and will involve no type I error adjustment. The subgroup analyses will be based on the primary analysis population for efficacy.

Regarding safety, subgroup analysis will be performed for overall number of treatment emergent adverse events (TEAEs), related TEAEs and serious TEAEs, overall TEE and mortality rates for the subgroups 2-6.

5.4 Missing data

Missing data will not be imputed except for analyses of the primary efficacy endpoint (see section 10.1 Primary efficacy analysis and 10.2 Secondary efficacy analyses for details) and partial and missing dates as specified below.

Partial or missing dates and times

Where the start date of an event or medical condition is missing or partially missing, the event will be assumed to be started after the start of IMP, unless there is clear evidence (through comparison of partial dates/times) to suggest otherwise.

In case of a partial or missing end date the medical condition will be assumed to be ongoing after start of IMP except if the partial date indicates that the condition stopped prior to start of IMP.

5.5 Observation and analysis times

Study days

Study day is defined as the number of days since start of infusion of IMP and, for a particular date, and is calculated as:

```
Study day = Assessment date - Date of start of infusion of IMP + 1.
```

Therefore, the date of infusion of IMP will be Day 1.

Study periods

Start and End of infusion and start and end of surgery define important timepoints during the course of the study. The following study periods are defined using these timepoints:

- Before start of infusion, comprises screening and baseline period: all observations until start of infusion of IMP
- Before start of surgery: from start of infusion till start of surgery
- During surgery: all observation during surgery
- After end of surgery to Day 4/discharge
- Follow-up: all observations after Day 4/discharge to end of study (day 45)

Definition of baseline values

The baseline value is in general defined to be the last value which was assessed before the start of infusion.

For INR the baseline value is defined as the INR value used for dose calculation.

Definition of analysis timepoints or time windows

The definition of analysis timepoints / time windows is specified in the following table.

| | Measurement | Analysis Timepoint | Time window |
|---|-----------------------|------------------------------|-------------------------|
| | Coagulation Factors | 30 min after end of infusion | 30 min ± 15 min |
| | · apha | 2h after end of infusion | $2 h \pm 15 min$ |
| | , O ^{CLU} | 4h after end of infusion | $4 h \pm 30 min$ |
| | i o' | 12h after end of infusion | $12 h \pm 1h$ |
| | open. | 24h after end of infusion | $24 h \pm 2 h$ |
| 2 | Virology | Day 9 | Day 9 - 2 days/+ 5 days |
| | Rate of TEE/Mortality | Day 4 | Day 4 |
| | | Day 21 | Day 21 ± 1 week |
| | | Day 45 | Day 45 ± 1 week |

Patient Accounting and Disposition 6

6.1 Patient accounting

The number and relative frequencies of patients in each analysis population as defined in section 4 Analysis Populations will be presented overall and by randomized treatment, country and site. The enrolled population will only be presented overall.

Furthermore the number and percentage of patients in each analysis population will be presented overall and by treatment group including individual reasons of exclusion from the respective analysis population.

A list of patients with all randomization assignment information will be generated in order to confirm that the randomization was performed according to the randomization plan

Major protocol deviations leading to exclusion from the per-protocol population are specified

The number and relative frequency of patients with major protocol deviations leading to exclusion from the per-protocol population will be presented by treatment group, country, and study site for RAND.

In addition, all deviations of the in-/exclusion criteria will be summarized by treatment group and study site for the RAND.

All patients with protocol deviations as specified above will be listed.

Propert

Demographics and Background Characteristics 7

Demographic and baseline characteristics as specified in detail below will be presented descriptively by treatment group.

A statistical testing for baseline differences is not considered appropriate in a randomized study. In randomized controlled studies, randomization ensures that, on average, the distribution of baseline covariates will be similar between the different treatment groups.

7.1 Demographics

-an (black), Asian, Other)
 an (black), Asian, Other)
 an (

- Pre-infusion anti-coagulation therapy
- History of TEE
- Type of planned surgery
- Estimated blood loss

7.3 Medical history

The diseases are coded according to Medical Dictionary for Regulatory Activities (MedDRA[®]) Version 18.1 or higher and will be classified as follows:

Previous medical conditions, i.e. medical conditions that stopped prior to start of treatment

Ongoing (concomitant) medical conditions, i.e. medical conditions still present after start of treatment

The frequency of diseases recorded from medical history will be presented after classification into previous and concomitant conditions by system organ class (SOCs) as well as the frequencies of preferred terms (PT) within each SOC. If patients have more than one disease within a SOC or PT they will be counted only once for the respective SOC or PT.

Additionally, all PTs occurring in the MedDRA SMQ "Embolic and thrombotic events" will be presented. For patients with a history of TEE, time (in months) since occurrence of last TEE event before enrollment will be presented with descriptive statistics.

Exposure and Compliance 8

8.1 Treatment groups

Treatments will be labelled as follows:

- . **KCentra**
- Octaplex

For the RAND and mITT, patients will be assigned to the treatment groups they were randomized to and for the SAF to the treatment they actually received.

The number and percentage of patients will be presented by treatment group, study site and analysis population analysis population.

Deviations from the randomized treatment will be presented in the protocol deviation listing, outwritter see section 6.3 Major protocol deviations.

8.2 Dosage

Descriptive statistics for the total dose of IMP per patient will be presented by treatment group for the RAND, mITT and SAF. Both dose (IU) and weight adjusted dose (IU/kg) will ordistribu be analyzed.

8.3 Infusion duration

The infusion duration will be calculated in minutes as:

Duration of exposure (minutes) = (time of stop of infusion – time of start of infusion) Descriptive statistics for the infusion duration will be presented.

8.4 Discontinuations from study therapy

The number and percentage of patients who discontinued the infusion prematurely will be presented by treatment group.

Patients who discontinued study prematurely will be listed by study site and treatment group (Annex V to the CSR according to ICH E3 [2]). The listing will include age, sex, last visit, day of discontinuation, duration of treatment, and reason of discontinuation.

8.5 Compliance

IMP will be infused at the study site under the guidance of the investigator. However, compliance will be analysed and number of subjects who have received a miscalculated dose will be evaluated.

9 **Previous and Concomitant Therapies**

Previous and concomitant medications are coded according to WHO drug dictionary (Version SEP 16) and stored with ATC codes and generic names.

Therapies will be classified as previous if they stopped before start of infusion and as concomitant if taken after start of first infusion.

The number and frequency of previous and concomitant medications will be given per ATC level 2. Additionally, previous anti-coagulant therapy will be presented per ATC level 3. If a patient has received more than 1 drug within an ATC class, he/she will be counted only once for this ATC class.

descriptive statistics on the dose level administered. The number of patients who did not receive Vitamin K will be presented, with the reason of non-administration. Property of Octapharma. Do not copy or distribute without with

090-SAP-LEX-209-V03 2021-01-06 Syneos Health

10 Efficacy

10.1 Primary efficacy analysis

The primary efficacy variable is the hemostatic efficacy as assessed by the IEAB. The hemostatic efficacy is to be assessed based on objective criteria in the categories 'excellent', 'good', 'moderate' or 'none'. Ratings of 'excellent' and 'good' will be considered as 'effective' hemostasis, while a rating of 'moderate' and 'none' will be considered as 'ineffective' hemostasis. For details on the derivation see CSP Section 7.2.1 (Assessments for Primary Efficacy Endpoints).

The dichotomous 'hemostatic success' variable will be used in the analyses. This variable will be imputed as 'ineffective' under the following two circumstances:

- If hemostatic efficacy value is missing, then hemostatic efficacy will be considered 'none' for the analysis. This can occur in the RAND population if the patient is randomized and not treated (or does not undergo surgery), also in the mITT population if the patient is treated but does not undergo surgery due to insufficient coagulation.
- If patient receives additional coagulation treatment (e.g. PCC, single coagulation factors, plasma) after initial IMP infusion, then hemostatic efficacy will be considered 'none' for the analysis.

To demonstrate that treatment with OCTAPLEX is clinically not inferior to treatment with Beriplex[®] P/N (Kcentra) with respect to hemostatic success, a two-sample, one-sided test of the pair of hypotheses: 20

- H₀: $p_{\kappa} p_0 \ge \delta$ (inferiority) H₁: $p_{\kappa} p_0 < \delta$ (non-inferiority) VS.

will be carried out with a type I error probability of $\alpha = 0.025$ and clinical non-inferiority margin of $\delta = 0.15$. Whereby p₀ and p_K present the probabilities of hemostatic success of OCTAPLEX and Beriplex[®] P/N (Kcentra) respectively.

Farrington's and Manning's test for difference in proportions will be used to assess the primary hypothesis in an interim and in the final analysis. One-sided p-values and the corresponding nominal and repeated confidence intervals for the difference in hemostatic success probabilities will be presented.

The primary analysis will be performed on the RAND population. Additional analyses will be performed using the mITT and PP populations.

All patient data related to the primary efficacy analysis will be listed.

Handling of Missing Data

Patients with missing information on the primary efficacy endpoint (for example, patient for whom the surgery was not initiated due to an insufficient coagulation), will be assessed as having no hemostasis (i.e., hemostatic efficacy will be considered 'none' for the analysis).

Sensitivity and Robustness Analyses

In order to assess the treatment effect using different assumptions from those in the RAND analysis, the primary efficacy analysis will also be performed using the mITT and PP populations.

In case of non-inferiority in the mITT and the PP populations a "tipping point" analysis will be done to determine the robustness of the results

Iteratively patients excluded from the mITT/PP analysis assigned to the control arm will be considered as treatment successes, and patients excluded from the mITT/PP analysis and assigned to the OCTAPLEX arm will be considered as treatment failures, to determine the number of such imputed outcomes required to "tip" the study result from positive to negative 3 in the RAND population.

A sensitivity analysis will be conducted in the RAND, mITT, and PP populations based on the hemostatic efficacy rating by the investigators at the end of surgery. This analysis will be conducted with the same methods as described above for the primary efficacy endpoint.

A concordance analysis (hemostasis agreement) will be done to assess the agreement between the assessment by the IEAB and the investigator assessment.

the assessment by the IEAB and the investigator assessment. **10.2 Secondary efficacy analyses** The secondary efficacy endpoints will be tested for differences between OCTAPLEX and Beriplex[®] P/N (Kcentra). No confirmatory hypotheses testing will be done. Treatment will be compared exploratorily, point estimates and corresponding 95% confidence intervals will be presented in addition to descriptive statistics.

The following measurements will be considered as exploratory secondary endpoints:

- Proportion of patients with an INR value of less or equal to 1.5 at 30 (\pm 15) minutes after the end of infusion.
- Change in coagulation factor levels from baseline to 30 (\pm 15) minutes after the end of infusion:
 - 0 Factor FII
 - Factor FVII
 - Factor FIX
 - Factor FX
- Proportion of patients receiving red blood cells (RBC) during the surgery

The primary analysis of secondary endpoints will be based on the RAND population, except V for the proportion of patients receiving RBC during surgery, this will be based on subset of patients undergoing surgery. Additionally, the same analyses will be done on the mITT and PP populations.

Farrington's and Manning's test for difference in proportions will be used to test the secondary variables on proportions. Point estimates and two-sided 95% confidence intervals will be presented in addition to descriptive statistics for these endpoints.

The change in the individual coagulation factors from baseline to 30 minutes after the end of infusion will be tested with the Wilcoxon rank-sum test between OCTAPLEX and Beriplex[®] P/N (Kcentra). The Hodges-Lehmann estimator of the median difference of the intra-individual change in the individual coagulation factors from baseline to 30 minutes after

the end of infusion between OCTAPLEX and $Beriplex^{\ensuremath{\mathbb{R}}}$ P/N (Kcentra) and the corresponding 95% CI will be calculated.

Missing data will not be imputed.

All patient data related to the secondary efficacy analyses will be listed.

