#### **3** INVESTIGATIONAL PLAN

#### 3.1 Primary and Secondary Endpoints

#### **3.1.1 Primary Endpoint**

The primary efficacy endpoint is the hemostatic efficacy rating at the end of the surgery.

Efficacy will be rated by the investigator at the end of the surgery in a blinded manner based on a 4-point hemostatic efficacy scale taking into account blood loss and transfusion requirements in the context of the surgery.

The hemostatic efficacy rating will also be assessed by an independent endpoint adjudication board (IEAB) consisting of clinical experts. See Section 7.2.1 for details. All adjudications will be conducted in a blinded manner and the IEAB will be provided with all relevant details (e.g., duration of surgery, co-medication, medical history, predicted and actual blood loss, and transfusion information) of the patient and the actual procedure performed covering the time period up to the end of the surgery, as documented in the anesthesia record. To ensure the effectiveness of blinding and avoid potential bias, the INR and PT values will not be provided to the IEAB. The dichotomized final adjudicated hemostatic efficacy rating from the IEAB will serve as the primary efficacy variable for the statistical analysis. The concordance or discordance of the investigator and the IEAB ratings will also be determined as part of the final analysis; the IEAB will be kept blinded to the investigator's rating.

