#### **3.3.11** Independent Committees

The primary efficacy endpoint will be the assessment of clinical hemostasis as assessed by the blinded IEAB. In order to adjudicate the primary efficacy endpoint, the IEAB will receive the pre-operative documented expected average and maximum blood loss (both recorded irreversibly prior to randomization), the estimated actual blood loss, and all information on any transfusions and administration of "rescue" clotting factor-containing products. Additionally the IEAB will be provided with all available Hgb and Hct values and information on volume of hemorrhagic would drainage. INR and PT values will not be provided to help ensure the effectiveness of blinding and avoid potential bias. IEAB will be blinded to Investigator's clinical hemostasis rating. A detailed description of the information to be provided to the IEAB will be developed with the clinical experts and will be included in an IEAB charter.

An IDMC will be established by the Sponsor and will routinely monitor safety in the study. The IDMC will also advise on the further conduct/stopping of the study one the interim analysis has been performed. Details are provided in Section 8.6 and Section 9.4.

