#### 6.1.6 Procedures After Surgery

The following assessments will be performed within 1 hour post-surgery end:

- Blood sampling for local lab (see Section 7.3.6)
- Document AEs, vital status (see Section 7.3), concomitant medications (see Section 4.2) • and transfusions (see Section 7.2.2.3).

- Hemostatic assessment (see Section 7.2.1)
- Hematoma assessment (see Section 7.2.2.5)
- Wound drainage evaluation

The time of surgery end is defined as the surgery end time of the principal procedure.

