The hemostatic efficacy rating will also be assessed by an IEAB consisting of clinical experts. All adjudications will be conducted in a blinded manner and the IEAB will be provided with all relevant details (e.g. duration of surgery, co-medication, medical history, predicted and actual blood loss, transfusion information, details of hemorrhagic wound drainage) of the patient and the actual procedure performed covering the time period up to the end of the surgery, as documented in the anesthesia record. To ensure the effectiveness of blinding and avoid potential bias, the INR and PT values will not be provided to the IEAB. The IEAB will also be blinded to Investigator's clinical hemostasis rating.

The hemostatic efficacy of the study treatments is to be assessed in the categories 'excellent', 'good', 'moderate' or 'none'. Ratings of 'excellent' and 'good' will be considered as 'effective' hemostasis, while a rating of 'moderate' and 'none' will be considered as 'ineffective' hemostasis. Study Protocol

No. LEX-209

Assessment should be guided by clinical experience, the specifics of the surgery actually performed, additional transfusion requirements and blood loss occurred during the surgery. The criteria below involve aspects of intraoperative blood loss and transfusions.

Hemostatic Efficacy Scale (assessment at the end of the surgery – as documented in the anesthesia record)\*:

- **Excellent**: Intra-operative blood loss and transfusion requirements were lower than or equal to the average expected ones for the type of procedure performed in a patient with normal hemostasis and of the same sex, age, and stature.
- **Good**: Intra-operative blood loss and transfusion requirements were higher than the average expected ones but lower or equal to the maximal expected blood loss and transfusion requirements for the type of procedure in a patient with normal hemostasis.
- **Moderate**: Intra-operative blood loss and transfusion requirements were higher than the maximal expected ones for the type of procedure performed in a patient with normal hemostasis, but hemostasis was controlled.
- None: Hemostasis was uncontrolled necessitating a change in clotting factor replacement regimen.

\* For all ratings (excellent, good, moderate and none), unexpected blood loss due to surgical complications will not be taken into consideration when assessing intra-operative efficacy. These include:

- 1. Direct injury to a vessel (artery or vein).

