## 7.2.2.3 Red Blood Cell, Plasma and Platelets Transfusions Initiated During the Surgery

The time, amount (units and mL) and reason of all intra-operative RBC, plasma, and platelet transfusions during surgery will be recorded and analyzed. All blood and plasma products given throughout the hospitalization for the original admission and the reason for their administration will be captured on a CRF page designed specifically for this purpose. This will include any blood product and/or volume expanders. Blood products will be defined as autologous blood, allogenic whole blood, whole blood, RBC, FFP, platelets, and cryoprecipitate (14) (American Society of Anesthesiologists 2006).

Cell saver blood is to be accounted for when assessing the volume of transfusions.

The ASA (American Society of Anesthesiologists) recommendations for triggering a RBC transfusion will be used to assess the need for RBC transfusions. These guidelines recommend RBC transfusion when Hg levels fall acutely below 6 g/dL and no transfusion when Hg levels are above 10 g/dL (14) (ASA 2006). The determination of whether intermediate Hgb concentrations (i.e., 6–10 g/dL) justify or require red blood cell transfusion should be based on any ongoing indication of organ ischemia, potential or actual ongoing bleeding (rate and magnitude), the patient's intravascular volume status, and the patient's risk factors for complications of inadequate oxygenation. These risk factors include a low cardiopulmonary reserve and high oxygen consumption indicated by decreased urine output, unstable vital signs, evidence of myocardial ischemia, increased lactate or base deficit, change in level of consciousness, orthostatic signs (dizziness or decreased blood pressure with standing), or with impending blood loss (expected for the scheduled surgery). If there is a deviation from this guideline the physician/surgeon will be asked to document the justification for any transfusion outside of these guidelines.

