# 9.2.2 In addition the primary endpoint will also be analysed using the mITT and the PP population. Efficacy Analysis Plan

### 9.2.2.1 Primary Endpoint: Hemostatic Efficacy

The primary efficacy variable is the hemostatic efficacy as assessed by the IEAB. The hemostatic efficacy is to be assessed based on objective criteria in the categories 'excellent', 'good', 'moderate' or 'none'. Ratings of 'excellent' and 'good' will be considered as 'effective' hemostasis, while a rating of 'moderate' and 'none' will be considered as 'ineffective' hemostasis.

The dichotomous 'hemostatic success' variable will be used in the analyses. This variable will be imputed as 'ineffective' under the following two circumstances:

- If hemostatic efficacy value is missing, then hemostatic efficacy will be considered 'none' for the analysis. This can occur in the RAND population if the patient is randomized and not treated (or does not undergo surgery), also in the mITT population if the patient is treated but does not undergo surgery due to insufficient coagulation.
- If patient receives additional coagulation treatment (e.g. PCC, single coagulation factors, plasma) after initial IMP infusion, then hemostatic efficacy will be considered 'none' for the analysis.

To demonstrate that treatment with OCTAPLEX is clinically not inferior to treatment with Beriplex® P/N (Kcentra) with respect to hemostatic success, a two-sample, one-sided test of the pair of hypotheses:

H0: 
$$p_K - p_O \ge \delta$$
 (inferiority)  
vs. H1:  $p_K - p_O < \delta$  (non-inferiority)

will be carried out with a type I error probability of  $\alpha = 0.025$  and clinical non-inferiority margin of  $\delta = 0.15$ . Whereby  $p_0$  and  $p_K$  present the probabilities of hemostatic success of OCTAPLEX and Beriplex® P/N (Kcentra) respectively.

Farrington's and Manning's test for difference in proportions will be used to assess the primary hypothesis in an interim and in the final analysis. One-sided p-values and the corresponding nominal and repeated CIs for the difference in hemostatic success probabilities will be presented.

The primary analysis will be performed on the RAND population. Additional analyses will be performed for the mITT and the PP population.

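### The rule that recodes hemostatic efficacy to none after additional coagulation treatment has a start but no end, although the endpoint is fixed at the end of surgery

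*SAP*

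**What the plan says.** Four features of the plan bear on this point.

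- **The endpoint.** Protocol 3.1.1: "The primary efficacy endpoint is the hemostatic efficacy rating at the end of the surgery". Under Protocol 7.2.1 the IEAB receives patient and procedure details "covering the time period up to the end of the surgery". Protocol 6.1.6 fixes that moment: "The time of surgery end is defined as the surgery end time of the principal procedure".
- **The override.** After the rating, the analysis applies a recoding. SAP 10.1: "If patient receives additional coagulation treatment (e.g. PCC, single coagulation factors, plasma) after initial IMP infusion, then hemostatic efficacy will be considered" none, which counts as ineffective. Protocol 9.2.2.1 has the same condition: "If patient receives additional coagulation treatment (e.g. PCC, single coagulation factors, plasma) after initial IMP infusion". Both state when the window opens; neither states when it closes.
- **The data.** Protocol 7.2.2.3 has the CRF capture "All blood and plasma products given throughout the hospitalization for the original admission and the reason for their administration". Post-operative plasma will therefore be in the database.
- **Windows used elsewhere.** SAP 10.3 limits its plasma and platelet endpoint to transfusions begun during surgery. SAP 5.5 defines separate periods during surgery and from the end of surgery to Day 4 or discharge. The override cites neither.

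**The concern.** The override is part of the derivation of the only confirmatory variable. Take a patient rated excellent who first receives plasma on Day 2. With a window that closes at the end of surgery, the patient is a success. Under the rule as written, the patient is a failure. Two statisticians could therefore derive different primary outcomes from the same data.

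The interim adds a second difficulty. SAP 12.3 cuts the data when the primary endpoint of the first 185 randomized patients is available. With an open window, a patient still in hospital could be a success at the interim and a failure at the final analysis. The change would come from treatment given after the endpoint had been assessed.

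If the end is left unstated, it could also be chosen after outcomes by arm are known.

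**Working it through.** **Inputs from the documents.** Margin 0.15, one-sided 0.025, planning rates 89% (Kcentra) and 85% (OCTAPLEX), 166 per arm raised to 185 for about 10% not treated or not operated on (SAP 3.1). Boundaries are 2.33216 (interim) and 2.07753 (final) (SAP 12.4). RAND is the primary population, with missing ratings counted as failures (SAP 10.1).

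**1. The plan's own figures.** Alpha spent at half information is 0.025 × (1 − e^0.4)/(1 − e^0.8) = 0.01003, so z = 2.325 (SAP: 2.33216, p = 0.00985). The final boundary comes out at 2.076 (SAP: 2.07753). A normal approximation to the two-look Farrington-Manning design needs 167 per arm (SAP: 166) and gives 79.97% power at 166 (SAP: 80.3%). 166/0.90 rounds up to 185. The sample size is not in question.

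**2. Assumption.** Let q be the share of end-of-surgery successes, equal in both arms, that first receive such a product after surgery. The documents give no value; q = 1, 3, 5 and 10% are shown as a range.

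**3. Model.** RAND success is 0.89 × 0.9 = 0.801 and 0.85 × 0.9 = 0.765; for equal true rates it is 0.801 in both arms. There are 185 per arm, with an interim look at 92 per arm. The test statistic is

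z = (p̂O − p̂K + 0.15)/SE0,

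where SE0 uses the estimates restricted to pK − pO = 0.15. The SAP boundaries apply and the non-binding futility rule is ignored. One million trials were simulated per scenario, and both codings were tested in each trial.

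| q | Power, literal reading, 89/85 | Conclusions differ, 89/85 | of which lost / gained under literal reading | Conclusions differ, 89/89 |
|---|---|---|---|---|
| 0 | 73.3% | – | – | – |
| 1% | 72.5% | 5.6% | 3.2 / 2.4 | 2.2% |
| 3% | 71.1% | 9.8% | 6.0 / 3.8 | 4.2% |
| 5% | 69.9% | 12.8% | 8.1 / 4.7 | 5.8% |
| 10% | 67.7% | 17.8% | 11.7 / 6.1 | 9.2% |

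The 73.3% in the first row is below 80% because untreated patients count as failures, not because of this rule. If 89% and 85% already include late recoding, nothing is lost against plan.

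**4. A single data set at the final analysis, n = 185 per arm.**

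- 148 vs 142 successes (Kcentra vs OCTAPLEX): z = 2.730, non-inferior.
- Remove 19 from each arm, 129 vs 123: z = 2.444, still non-inferior.
- Remove 4 from OCTAPLEX only, 148 vs 138: z = 2.202. Remove 5, 148 vs 137: z = 2.072, below 2.07753.
- From equal arms (148 vs 148, z = 3.547), 11 one-sided recodings are needed.

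**5. When the true end-of-surgery difference equals the margin.** Equal recoding multiplies both rates by (1 − q), and so the difference as well. With RAND rates of 89% vs 74% and 185 per arm (no further allowance for untreated patients), 0.15 becomes 0.15 × 0.95 = 0.1425 at q = 5%, and 0.15 × 0.90 = 0.135 at q = 10%. The chance of claiming non-inferiority rises from 2.5% to 3.6% and 5.0%.

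**The case against.** The strongest reply is that context settles the reading. The override imputes a dichotomized end-of-surgery rating, and the IEAB file stops at the same point. The same list of products appears in Protocol 4.2.3, for additional treatment before the operation. That makes a closed window the likelier intent. It remains inference: the override is applied after the rating, so the IEAB's window does not limit it.

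The reply is also right about size. The values of q have no anchor in the documents, 89%/85% is described as conservative, and discordance counts changes both ways. At 1, 3 and 5% the net power cost is 0.8, 2.2 and 3.4 points. Tipping a clear result takes one-sided recoding, and nothing in this double-blind plan points to that. The interim worry is narrow, since it affects only patients first treated after the cut-off.

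Three stronger readings are tempting but not supported.

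- **That the override itself is wrong.** The trial that supplies the margin also used the need for additional coagulation-factor products as a criterion (Protocol 1.1.2.1). The scale's own lowest category is "Hemostasis was uncontrolled necessitating a change in clotting factor replacement regimen", and the IEAB sees rescue products (Protocol 3.3.11). Some recoded patients would be rated none anyway.
- **That the lack of an analysis without the override is an error.** The plan already has mITT, PP, investigator-rating, concordance and tipping-point analyses. An IEAB-rating analysis without the override would be an optional addition.
- **That type I error is inflated.** See the verdict.

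**Conclusion.** The point holds as a gap in the definition of the primary variable, and it should be fixed. Followed as written, the rule can turn a true end-of-surgery success into a failure because of later treatment, and no passage prevents this.

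The true size is unknown. Under equal late recoding of 1 to 10% on RAND, the net power loss at 89%/85% is 0.8 to 5.6 points (73.3 − 72.5 and 73.3 − 67.7). The two readings disagree in about 2 to 9% of trials at equal true rates, or 6 to 18% at 89%/85% in both directions together. These are consequences of assumed rates, not estimates for this trial.

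A reader might infer from the rise to 3.6% or 5.0% that the test exceeds its level. It does not for the variable as literally defined, whose true difference in those scenarios is 14.25 or 13.5 points and so lies inside the margin. The rise shows only that the literal variable answers a different question from the end-of-surgery endpoint.

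**What to change.** For analysis only, in SAP 10.1 and Protocol 9.2.2.1:

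1. Limit the recoding to products given from IMP infusion to the end of surgery as defined in Protocol 6.1.6.
2. State that the same window applies at the interim and final analyses, and set it before unblinding.
3. Leave patients whose surgery never starts as failures through the existing missing-rating rule, so that they need no separate window.
4. Tabulate, per arm, recoded patients and post-operative product use by timing, and by reason where recorded.

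The cost is one phrase in each document and one table. Sample size, boundaries and treatment do not change. The small downside is that post-operative use no longer counts in the primary variable; the table keeps it visible. Reasons may be incomplete for post-operative PCC or single factors, because the blood-product list in Protocol 7.2.2.3 does not name them.
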